There are four purposes to this study. The primary purpose of this study is to evaluate the impact of walking as an exercise component of VR on both primary and secondary vestibular-specific outcome measures. The primary outcomes are mCTSIB, TUG test, DGI, and DHI, while the secondary outcomes are the total number of visits and length of interventions (in weeks). The second purpose is to evaluate whether pedometers increase the adherence of older adults with vestibular issues to a walking program. This will be measured by change in physical activity, as represented by International Physical Activity Questionnaire (IPAQ) Walking Metabolic Equivalent of Task (MET)-minutes/week and IPAQ Total Physical Activity MET-minutes/week scores from the IPAQ short form during the episode of care (admission and discharge) and on four-weeks follow-up compared to those patients who only received instructions to walk without a pedometer. The third purpose of this study is to establish test-retest reliability of the TUG test on older adults with dizziness. Lastly, the fourth purpose of this study to investigate if the TUG, DGI, and mCTSIB are significant and strong predictors of the DHI in older adults with dizziness. Protocol #1365169 “Predictors of Disability in the Older Adults” is being performed to supplement the number of subjects for the fourth objective of this study.

Study Design

Research Design

1. Experimental Design. To answer the first and second study objectives, a pragmatic, randomized, prospective, clinical study on 54 older adults with dizziness will be utilized. This will be conducted at Florida Hospital Sports Medicine and Rehabilitation locations that offer vestibular therapy. These are in East Orlando and Winter Park.
2. Correlation Design. A correlation analysis will be performed on the data collected on 54 subjects in the experimental design to establish the test-retest reliability of the Timed Up and Go.
3. Cross-sectional Descriptive Design. A regression analysis will be performed on three predictors of the Dizziness Handicap Inventory, obtained from the data collected on 54 subjects in the experimental design and from Florida Hospital Sports Medicine and Rehabilitation Physical Therapy medical charts from June 2015 to June 2018 that met the inclusion and exclusion criteria that were outlined in the Protocol #1365169.

Study Agent, Device, and/or Intervention Description

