The VR (control) group will follow the conventional VR physical therapy without the encouragement of walking and without specification of walking in the home exercise program.

The use of an assistive device can be recommended for any subject in any group by the research staff to maximize safety. The patient may need to purchase the assistive device.

Participants who do not belong to the intervention group with pedometer will receive a pedometer after they completed the study. They will receive instructions on how to use the pedometer prior or on the day of their last visit.

Study Visits

For the experimental design that will be conducted at Florida Hospital locations, the following data will be collected as standard of care by the physical therapist during initial evaluation, and if more time is needed, during the first follow-up physical therapy appointment: mCTSIB, TUG, DGI, DHI, age, gender, body mass index, home situation, Functional Comorbidity Index (FCI) total, ability to drive, medications and insurance type. After the subject signs the informed consent, the study coordinator will be notified by the research staff to conduct a retrospective chart review on the physical therapy initial evaluation and first follow-up visit, if applicable, of the subject. The study coordinator will extract the following baseline measurements from the subject's medical record: DGI, mCTSIB, DHI, TUG and socio-demographic data that include age, gender, body mass index, home situation (lives alone or with social support), Functional Comorbidity Index (FCI) total, ability to drive (able or unable), medications for vertigo and insurance type (Medicare/Non-medicare). Based on the retrospective chart review, the study coordinator will determine if the subject is eligible to participate in the study.

Visit 1: Once the study coordinator determined that the subject is eligible to participate in the study, the subject will be assigned a research number and will be randomized into one of the three intervention groups. The research staff can initiate or continue the VR program. For the test-retest reliability of the TUG test, there will be one practice trial followed by two final performances that will be included in the data analysis. The subject will also be asked to complete the IPAQ-short form questionnaire. The test-retest reliability of TUG and the IPAQ-short form questionnaire are for research purposes only.

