All statistical analyses were performed using SPSS version 26. Mean and standard deviation were used to describe interval and ratio data, and frequencies for nominal data. Statistical significance was set at alpha <0.05. Since the parameters of a normal distribution were not met, nonparametric statistical tests were chosen for statistical analysis.

Objective 1. To evaluate the impact of walking as an exercise component of VR on both primary and secondary vestibular-specific outcome measures.

Mean and standard deviations on the mean differences of pretest and posttest of TUG, DGI, DHI, and mCTSIB were calculated to compare walking (VRWP + VRW) and control groups (VR only). P-value was calculated using the Kruskal-Wallis test to check for between-group differences in the primary and secondary outcomes. For within-group differences, the Wilcoxon Signed Rank Test was used to examine significant differences between the pretest and posttest.

Objective 2. To evaluate whether pedometers increase the adherence of older adults with vestibular issues to a walking program.

To compare the VRWP, VRW and VR groups, IPAQ-Walk and IPAQ-Total scores were categorized as improve, same or decline in pretest and posttest, posttest and four-weeks follow-up, and pretest and four-weeks follow-up. P-value was calculated using the Kruskal-Wallis test to check for between-group differences of sociodemographic data, IPAQ-Walk, IPAQ-Total, compliance in meeting step goals and compliance in step log. Friedman's 2-way ANOVA by ranks test was used to examine significant differences within the group.

Objective 3. To establish test-retest reliability of the TUG test on older adults with dizziness.

Intraclass Correlation Coefficient (ICC) was calculated using the two-way mixed model, consistency type on a single measure model with a 95% CI for relative reliability. For absolute reliability, the Standard Error of Measurement (SEM), Minimal Detectable Change (MDC) 95% CI, and Bland-Altman 95% level of agreement were examined. The SEM provides the range of scores on retesting. A smaller value of SEM means the calculated score is close to the true score.⁴⁴ The MDC is used to reflect the true change in score that exceeded the errors of measurements. Both the SEM and MDC are the same units of the original measures, which allows easier interpretation of results when applied in the clinical practice.⁷⁴

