The Bland-Altman plots show the distribution of the difference scores of two measurements around zero. The 95% level of agreement means that 95% of the difference scores fall within two standard deviations above or below the mean of the difference scores. Values closer to zero means greater reproducibility between two repeated measures.

Objective 4. To investigate if the TUG, DGI, and mCTSIB are significant and strong predictors of the DHI in older adults with dizziness.

The subjects were then grouped based on the DHI test results, using the categories suggested by Whitney et al: 0-30 for mild, 31-60 for moderate, and 61-100 for severe.¹⁰⁴ This analysis is similar to the work of Vereeck et al⁸⁴ to obtain a better picture between the dependent variable DHI and the independent variables: mCTSIB, TUG, and DGI. Kruskal-Wallis analysis was calculated to compare group means for age, mCTSIB, TUG, and DGI. The significance values were adjusted by the Bonferroni correction for multiple tests.

Before the multiple linear regression analysis, assumptions were tested to establish the nature of the data. The obtained Durbin-Watson statistic for the analysis of the independence of

observations is 2.639. The Durbin-Watson statistic can range from 0 to 4, with a value of approximately 2 to indicate that there is no correlation between residuals. The obtained value is close to 2, therefore it can be accepted that there is the independence of observations. The assumptions of homoscedasticity, normality, and multicollinearity are upheld. There is no presence of outliers in the data.

The Spearman Rho correlation coefficients were calculated to establish the relationships between the DHI and mCTSIB, TUG and DGI. As a general guideline, the value 0.00 to .25 indicates little to no relationship, 0.25 to 0.50 suggests fair relationship, 0.50 to 0.75 denotes moderate to good relationship and above .75 is considered good to excellent relationship.⁴⁴ Then, a multiple linear regression analysis was conducted for a continuous dependent variable and three independent variables to identify the predictors of DHI.

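### The TUG test-retest ICC is of the consistency type, so a systematic shift between the two trials, if there is one, drops out of the ICC and possibly out of the SEM and MDC

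*Combined protocol and SAP*

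**What the plan says.** Under Study Visits, Visit 1, the plan states that "there will be one practice trial followed by two final performances that will be included in the data analysis". The Research Design section gives the sample: "A correlation analysis will be performed on the data collected on 54 subjects in the experimental design to establish the test-retest reliability". The prospective Statistical Analysis Plan names an ICC for this purpose but not its form, and mentions no SEM, MDC or Bland-Altman analysis.

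The later Data Analysis section, under Objective 3, supplies the form: a "two-way mixed model, consistency type on a single measure model", reported "with a 95% CI for relative reliability". It treats absolute reliability separately: "the Standard Error of Measurement (SEM), Minimal Detectable Change (MDC) 95% CI, and Bland-Altman 95% level of agreement were examined". No formula is given for the SEM or the MDC. On use, it says "The MDC is used to reflect the true change in score that exceeded the errors of measurements", and it describes the SEM as telling the reader what range of scores to expect on retesting.

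On the plot, "The Bland-Altman plots show the distribution of the difference scores of two measurements around zero", and the limits are explained as meaning that "95% of the difference scores fall within two standard deviations above or below the mean of the difference scores". No ICC, SEM, MDC, TUG standard deviation or mean between-trial difference appears in the documents.

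**The concern.** A consistency ICC asks whether subjects keep their relative positions from one trial to the next. If everyone is half a second faster on the second trial, it counts no error. The plan's own account of the SEM, as the spread to expect on retesting, is closer to agreement: does the same person get the same time again? An SEM equal to the square root of the residual mean square, or to the within-trial SD times the square root of one minus this ICC, leaves the shift out. An MDC built on that SEM does too.

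A shift in either direction is plausible. The subject performs three TUGs (one practice, two analysed), so learning, fatigue or provoked symptoms could move the second analysed time. The Potential Risks section itself lists dizziness as a risk of the test.

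At stake is the main product of Objective 3. The Background says no study has tested TUG test-retest reliability in older adults with dizziness, and the Study Outcome Measures section says no MDC is established for them. Later users may adopt the figure as a threshold in seconds. The randomised comparisons do not depend on it.

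**Working it through.** There is no reported figure to reproduce, so the check is algebraic, with assumed inputs.

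**Inputs.** From the documents: two analysed trials, 54 planned subjects, ICC form as quoted. Assumed: between-subject SD sb of 2 to 4 s, random error SD se of 0.6 or 1.0 s, mean shift d (trial 2 minus trial 1) of 0, 0.25, 0.5 or 1.0 s. The sign of d does not matter, because only its square enters the ICC, SEM and MDC.

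**Formulas.** With two trials, the trial means lie d/2 either side of their average, so the trial variance is d²/2.

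- Consistency ICC = sb²/(sb² + se²)
- Agreement ICC = sb²/(sb² + se² + d²/2)
- Residual-based SEM = se
- SEM with trial variance = √(se² + d²/2)
- MDC95 = 1.96 × √2 × SEM = 2.772 × SEM
- Limits of agreement = d ± 1.96 × √2 × se

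**SEM and MDC.**

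| se (s) | d (s) | SEM with trial variance (s) | MDC95, residual-based (s) | MDC95 with trial variance (s) | Rise |
|---|---|---|---|---|---|
| 0.6 | 0 | 0.600 | 1.66 | 1.66 | 0% |
| 0.6 | 0.25 | 0.626 | 1.66 | 1.73 | 4% |
| 0.6 | 0.5 | 0.696 | 1.66 | 1.93 | 16% |
| 0.6 | 1.0 | 0.927 | 1.66 | 2.57 | 55% |
| 1.0 | 0 | 1.000 | 2.77 | 2.77 | 0% |
| 1.0 | 0.25 | 1.016 | 2.77 | 2.81 | 2% |
| 1.0 | 0.5 | 1.061 | 2.77 | 2.94 | 6% |
| 1.0 | 1.0 | 1.225 | 2.77 | 3.39 | 22% |

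**ICC.** The smallest fall for shifts of 0.5 to 1.0 s is at sb = 4, se = 1.0, d = 0.5: 16/17 = 0.941 becomes 16/17.125 = 0.934, a drop of 0.007. The largest is at sb = 2, se = 0.6, d = 1.0: 4/4.36 = 0.917 becomes 4/4.86 = 0.823, a drop of 0.09.

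**Wider range.** Take instead a single-score SD of 3 to 5 s and a consistency ICC of 0.80 to 0.98, so that se = SD × √(1 − ICC). The MDC then rises by 0.3 to 8% for a 0.25 s shift, 1 to 30% for 0.5 s and 5 to 94% for 1.0 s.

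**Simulation.** With 54 subjects, SD 5 s and true consistency ICC 0.95 (4,000 runs per shift), the mean consistency ICC stayed at 0.948 to 0.949 for every shift. The mean agreement ICC was 0.948, 0.947, 0.944 and 0.929 for shifts of 0, 0.25, 0.5 and 1.0 s. The residual-based SEM stayed at about 1.11 s throughout, so it does not respond to the shift.

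**Would Bland-Altman reveal it?** At se = 0.6 s the limits move from −1.66/+1.66 s with no shift to −0.66/+2.66 s with a 1.0 s shift. The standard error of the mean difference is √2 × se/√54, which is 0.12 s at se = 0.6 and 0.19 s at se = 1.0. A 0.5 s shift is therefore at least 0.5/0.192 = 2.6 standard errors from zero. A 0.25 s shift at se = 1.0 s is only 1.3 standard errors, but there it changes the MDC by 2%.

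**The case against.** The strongest reply is that the plan does not present this ICC as a measure of agreement. It labels it relative reliability and gives absolute reliability its own statistics, including limits centred on the mean difference in a plot read against zero. That stands: a shift large enough to matter would be visible there, as shown above. What it does not do is alter the ICC or a single MDC figure, and those are what others will quote.

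Second, the SEM formula is unstated. An SEM taken from the one-way within-subject mean square has expected square se² + d²/2 and already contains the shift. This also stands, so the effect on the SEM and MDC is conditional.

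Third, the practice trial should reduce a learning shift. It does, but it does not exclude fatigue or symptom provocation.

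Fourth, a constant order effect is bias rather than random noise. If the TUG is run the same way at admission and discharge, the effect largely cancels from the change score to which an MDC is applied, so leaving it out of the MDC is defensible. This has force. However, Study Visits does not describe the trial structure of the TUG at initial evaluation or discharge, so cancellation cannot be assumed. The sensible answer is to show both values rather than replace one with the other.

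A reader might infer that the reported reliability is inflated, or that the MDC is too small and labels noise as true change. The documents do not support that: they report no shift, ICC, SEM or MDC, and do not say how the last two were computed.

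**Conclusion.** The point holds conditionally. It is certain that the stated ICC form ignores a between-trial shift, and that the prospective Statistical Analysis Plan left the form open. It is unknown whether a shift occurred and whether the SEM and MDC omit it. If both are so, the MDC understatement runs from negligible at a quarter of a second to substantial at a full second. Every percentage rests on assumed standard deviations and shifts, and the highest ones need a small random error together with a large shift. Nor would it be right to conclude that a shift is concealed, since the Bland-Altman analysis keeps it. Severity is minor, and would rise only if the mean trial difference proves material.

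**What to change.** In Data Analysis, Objective 3:

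1. Report the two-way absolute-agreement single-measure ICC with its 95% CI as the test-retest coefficient, with the consistency ICC beside it.
2. Report the mean trial 2 minus trial 1 difference with its 95% CI. This tells the reader at once whether the choice of ICC matters.
3. State the SEM and MDC95 formulas. Give the SEM and MDC95 with trial variance included as a companion to the residual-based values, setting a negative trial-variance estimate to zero.

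The cost is one changed option in the SPSS reliability procedure and a few extra lines in the table, on data already planned. The downside is that the reported ICC and MDC may be slightly less favourable.

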The principal investigator may share the research data with accreditation organizations and regulatory agencies, dissertation committee, and publications, medical meetings, or scientific journals for the purposes of completing the research study, and analyzing and evaluating the results. Individual patients (subjects) will not be identified during data sharing, and a research number will be used instead during the data sharing process, unless necessary to carry out the research study or required by law.

Sample Size Determination

A priori power analysis predicting a large effect size ($F=.25$) determined that a total of 54 subjects (18 in each group), who met the inclusion and exclusion criteria will be needed, with alpha at the conventional value of .05 to achieve a .80 power, that includes an assumption of a dropout rate of 10% .

Statistical Analysis Plan

The results will be presented through the following tables with supporting explanations:

- Clinical and sociodemographic characteristics of participants by group at baseline.
- Comparisons of TUG, DGI, mCTSIB and DHI between the three intervention groups on admission and discharge.
- Comparisons of self-reported walking activity (walking MET-min/week) and total self-reported energy expenditure (total physical activity MET-min/week) as determined from the IPAQ short form on admission, discharge and four-week follow-up between the three intervention groups
- Comparisons of averages of compliance to step log recording and compliance rate for meeting step goal between the VRWP and VRW groups. Compliance is defined as low (<33%), moderate (33%-75%) and high (>75%) based on the step log or walking log. This grading of compliance was used by Hall and colleagues in their research on efficacy of gaze stability exercises in older adults with dizziness.⁵³
- Comparisons of total number of visits and length of interventions in weeks between the three intervention group.
- Intraclass Correlation Coefficients for the Timed Up and Go test-retest reliability
- Result of stepwise linear regression analysis for TUG, DGI, mCTSIB and DHI

All interval and ratio data will be tested for normality prior to undertaking the data analysis. Descriptive statistics will be used to describe the characteristics of the sample and compare the three groups at baseline. This will include Analysis of Variance (ANOVA) for parametric and Chi Square for nonparametric sociodemographic and clinical data.

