Analyses will employ five repeated measures Analysis of Covariance (ANCOVA), adjusting for age, with two independent variables (group and time) and five outcome measures (TUG, DGI, DHI, mCTSIB and IPAQ short form). The adjustment of age is based on age-related decline. Intraclass Correlation Coefficient will be calculated to establish the test-retest reliability of the TUG and a stepwise linear regression with age as covariate will be conducted for all 54 subjects at baseline to determine if TUG, mCTSIB and DGI are predictors of DHI. Two-tailed test will be utilized to compare the compliance with step log recording and meeting step goals between the two walking groups (VRWP and VRW), and ANOVA to compare of total number of visits and total length of intervention in weeks between the three groups. Alpha for all analyses will be set at 0.05 to test for significant difference.

Potential Risks and Benefits

Potential Benefits

Possible benefits include improved physical function.

Potential Risks

The addition of a prescribed walking program in the treatment of dizziness will challenge the subject's balance, and in rare cases may result in falls or more dizziness.

Performance-based outcomes such as mCTSIB, DGI, and TUG check for the subject's reaction whenever in a condition of unsteadiness. The risks associated with these tests are the potential for falls and for dizziness. Self-report questionnaires such as the DHI and IPAQ will need the subject to read the questions and recall past experiences. Looking down and reading the questions may provoke dizziness and eye strain. Other possible risks for subjects are: 1) finding the questions to be sensitive 2) emotional discomfort (uncomfortable/embarrassed/sad/tired) and 3) distress as subject thinks of experiences.

Mitigation of Risks

The research staff (treating physical therapist) will supervise the treatment at all times to minimize any such risks.

Provisions to Protect the Privacy Interest of Subjects

Subjects will be assigned research numbers for study-related records and data sharing. The patient's confidentiality will be protected by observing the HIPAA policies and procedures.

Early Withdrawal of Subjects

Investigator Withdrawal of Subjects

The PI may terminate the participation of the subject in the study if the subject may be in any danger or no longer meets the inclusion criteria of the study.

Subject Request for Withdrawal from Study

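### Objective 4: a Durbin-Watson value of 2.639 does not support the stated independence at the planned n of 54, and the planned age adjustment and the analysis set are left unstated

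*Combined protocol and SAP*

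**What the plan says.** Data Analysis, Objective 4, reports that the Durbin-Watson statistic for independence of "observations is 2.639", notes that a value of about 2 means uncorrelated residuals, and then states: "The obtained value is close to 2, therefore it can be accepted that there is the independence of observations". No sample size, number of predictors, row order, critical value or p-value accompanies the figure.

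The same section describes "the dependent variable DHI and the independent variables: mCTSIB, TUG, and DGI" and ends by saying that "a multiple linear regression analysis was conducted for a continuous dependent variable and three independent variables". Age appears only in the Kruskal-Wallis comparison of the DHI severity groups.

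The Statistical Analysis Plan specified something different: "a stepwise linear regression with age as covariate will be conducted for all 54 subjects at baseline".

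On the analysis set, Study Objectives says that a separate chart protocol "is being performed to supplement the number of subjects for the fourth objective of this study". Research Design, item 3, adds charts from June 2015 to June 2018 that "met the inclusion and exclusion criteria that were outlined in the Protocol #1365169". The number of charts is not given.

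**The concern.** There are three linked points.

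- A distance of 0.639 from 2 is judged by eye. How far the statistic strays from 2 by chance depends on n, and at 54 subjects 2.639 is an unusual value.
- The planned age adjustment appears to have gone, with no reason given. If it has, a balance test can look predictive of DHI partly because it carries information about age.
- The plan gives two analysis sets, and the report of the analysis gives none.

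A reader is told that independence was verified by a figure that does not verify it. Neither 2.639 nor the DHI coefficients can then be checked against the plan. Objective 4 is one of four stated purposes, and the Publication Plan foresees a paper for each.

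**Working it through.** **Inputs.** Durbin-Watson d = 2.639 and three predictors (Data Analysis, Objective 4); n = 54 and age as covariate (Statistical Analysis Plan); alpha .05 (both sections). The sidedness of the test is not stated.

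**The reported figure.** Without residuals 2.639 cannot be recomputed, so it is taken as given. It implies a lag-1 residual autocorrelation of about 1 − 2.639/2 = −0.32.

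**Bounds test.** For values above 2, compare 4 − d = 4 − 2.639 = 1.361 with the lower bound dL. Below dL the test rejects whatever the predictor values; between dL and dU it is inconclusive. Bounds are from the exact (Imhof) distribution with an intercept, 2.5% per tail:

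- n = 54, three predictors: dL 1.367, dU 1.598. 1.361 < 1.367, so it rejects, narrowly.
- n = 53, three predictors: dL 1.360, dU 1.595. Inconclusive.
- n = 54, four predictors (age added): dL 1.328, dU 1.641. Inconclusive.

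With 5% in the upper tail only, the rejection limits 4 − dL at n = 54 are 2.554 (three predictors) and 2.593 (four). The value 2.639 exceeds both.

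**Typical p-value.** The exact p depends on the predictor values, so the median two-sided p over random designs is shown:

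| n | three predictors | four predictors |
|---|---|---|
| 30 | .070 | not run |
| 35 | .051 | .050 |
| 36 | .046 | not run |
| 40 | .037 | not run |
| 54 | .015 | .015 |
| 80 | .003 | .003 |
| 100 | .001 | .001 |

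At n = 54 the p-values across these designs run from .012 to .019 (three predictors) and .010 to .020 (four). The widest range that any design allows is .004 to .047 and .002 to .068. As a rough check, z = (2.639 − 2)/(2/√54) = 0.639/0.272 = 2.35.

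**What the statistic can show here.** Reshuffling 54 independent rows gives a central 95% range of 1.48 to 2.52, with 2.639 or more in 0.8% of orders. The value belongs to the row order as much as to the data.

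It is also blind to the dependence most plausible in this study. With 27 patients per site (the estimate under Study Site(s)/Location(s) and Number of Subjects), an assumed site intraclass correlation of .2 and sites mixed in row order, it falls outside 1.48 to 2.52 in 5.3% of data sets, about the rate with no clustering. Sorting rows by site raises this to 16.9%.

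**Age.** All correlations here are assumed: n = 54, the three tests correlated .5 with each other, a standardised age effect on DHI of .2 to .3, DGI and mCTSIB effects of 0 or .3, and TUG with no effect of its own. Rejection rate for TUG at nominal .05 when age is left out:

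- age equally correlated with all three tests (.3 to .5): .051 to .094
- age somewhat more correlated with TUG (.4/.3/.3, .5/.4/.4 or .5/.3/.3): .061 to .163
- with age entered: .046 to .054

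The cost of entering age is a standard-error ratio of 1/√(1 − r²), where r is the partial correlation of TUG with age given the other two tests. For .5/.3/.3, r² = .30²/(.667 × .88) = .153, giving 1.09. For .3/.3/.3, r² = .10²/(.667 × .88) = .017, giving 1.01.

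**Analysis set.** The Statistical Analysis Plan uses the 54 trial subjects, Research Design item 3 uses those plus charts, and Data Analysis gives no n. The chart window (to June 2018) overlaps trial enrolment (January to August 2018) in the same rehabilitation service, and baseline scores are recorded as standard of care. A trial patient's chart could therefore also enter the chart sample.

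**The case against.** The strongest reply is that the analysed n is unknown. The failure is shown at the planned 54; at 30 subjects p would be about .07. The bounds result rests on 1.361 against 1.367, and it becomes inconclusive at 53 subjects or in the model with age. This is right. But an inconclusive test does not license accepting independence either, the typical p at 54 is about .015 in both models, and pooled charts would only raise n.

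Second, the Data Analysis section looks like an excerpt. It cites references 74, 84 and 104 while the list ends at 53, and Objective 4 opens as if following earlier text. The n and the decision on age may be stated in a fuller report. That possibility stands, but the independence sentence is complete and draws its conclusion from the figure alone.

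Third, the omission of age is inferred. The plan itself counts three predictors and treats age as a covariate, so the phrase in Data Analysis does not strictly exclude it. This also stands, and the fix allows for it. The age simulation rests on assumed correlations, and near-equal age correlations give rates close to nominal.

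Fourth, if Durbin-Watson says little here, a failed value has little inferential consequence. Agreed: no error in the DHI regression is shown. The fault lies in offering the figure as proof.

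**Conclusion.** The concern holds. At the only n that the documents state for this regression, 2.639 is not compatible with the reading given to it: two-sided p is typically about .015, and above .05 only at about 35 subjects or fewer. Dependence between subjects and wrong standard errors are not demonstrated.

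The planned age covariate appears to be absent without explanation, and the analysis set is inconsistent in the plan and unstated in the report. Under the assumed correlations, leaving age out puts the false-positive rate for a test with no effect of its own at about .05 to .16, against about .05 with age entered.

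The effect is limited to Objective 4 and does not reach the randomised comparison. It should be corrected because the correction is cheap and can change the DHI coefficients.

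**What to change.** - Delete the sentence that accepts independence from 2.639. Justify independence by design (one row per patient), and add a fixed site term as a sensitivity analysis. With two sites, cluster-robust standard errors would rest on two clusters and are not a substitute.
- If Durbin-Watson is kept, report it with n, number of predictors, row order and p-value.
- Regress DHI on age, TUG, DGI and mCTSIB entered together, or state that age was already in the model and report its coefficient. Explain any departure from the planned stepwise procedure.
- State one analysis set, with its n, consistently in Study Objectives, Research Design, Statistical Analysis Plan and Data Analysis.
- If charts are pooled, add a data-source indicator and confirm by medical record number that each patient enters once, unless Protocol #1365169 already ensures this.

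The cost is wording plus one regression re-run. Age and the trial subjects' medical record numbers are already held (Study Visits; Randomization), and site is known from where each patient was treated. Entering age widens the intervals by about 1% to 9% under the same assumed correlations, before any gain from lower residual variance.
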